### STATISTICAL ANALYSIS PLAN

SAS Code for Nonbinding Beta Boundary

```
proc seqdesign altref=0.3 errspend BOUNDARYSCALE=pvalue;
onesidederrorspending: design nstages=3 info=cum(3.6 8 20)/*3/20,
10/20=1/2, 1*/
method(alpha)=tri(tau=.65)
method(beta)=tri(tau=.65)
alt=upper stop=both (betaboundary=nonbinding)
alpha=0.025 beta=0.10;
samplesize model = twosamplefreq (nullprop=0.4 test=prop);
ods output Boundary=Bnd_Prop_pt5 ;
run;
```

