# STATISTICAL ANALYSIS PLAN

Method, which is a special case of Unified Family (Power) boundaries. A shape parameter of 0.65 will be used, and both boundaries will be non-binding.

Interim analyses will occur when approximately 20 and 60 total subjects have been enrolled and have had their 3-month assessment. The Latera response rate has been observed at approximately 85% in single-arm trials and is likely to be slightly lower in a single blind setting. Thus, 70% is likely a conservative estimate. The placebo response rate observed in pain trials is approximately 30%, and may be even higher in a procedural setting, so 40% was selected for the control response rate used in the study design calculations.

Assuming up to a 10% drop out rate and a 10% potential retrieval rate, the sample size is adjusted to enroll up to 150 subjects to assure adequate sample size with 3 months follow up.

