#### 5.4.4 Interim Analyses

There will be two planned interim analyses and one final analysis for this study (**Table 1**, below). The stopping boundaries are derived using the Triangular Method [see footnote 1], which is a special case of Unified Family (Power) boundaries. A shape parameter ( $\tau$ ) of 0.65 will be used, and both boundaries will be non-binding. Interim analyses will occur when approximately 22 and 60 total subjects have been enrolled with 3-month assessments. The stopping boundaries are

ST 800-A

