### STATISTICAL ANALYSIS PLAN

moderately aggressive for both effectiveness and futility to reduce the number of subjects enrolled if clear evidence of effectiveness or futility becomes apparent during the trial. When the design assumptions are correct (40% versus 70%), the chance that the trial will stop for effectiveness at the second interim analysis is about 1 in 3. However, if the Latera rate is 85% as seen in the single arm studies, the chance of stopping for effectiveness at the second interim analysis is better than 8 in 10. While all evaluable subjects enrolled at the time of the interim analysis would be followed through 3 months and included in the primary endpoint, an early termination at the second interim analysis could save 20-30% of the total sample size, depending on the enrollment rate.

Interim analyses will be carried out by an independent statistician and reviewed by the independent DMC. The interim analyses will use an alternative to the critical ratio test given below and described by Fleiss. The test results will be compared to the triangular group sequential boundaries. Additional operational details will be found in the DMC Charter.

$$z' = \frac{|p_2 - p_1| - \frac{1}{2}(1/n_{1.} + 1/n_{2.})}{\sqrt{\frac{p_1 q_1}{n_{1.}} + \frac{p_2 q_2}{n_{2.}}}}.$$

			ndaries value)	Cumulative Error Spending		
Analysis	Evaluable (n)	Futility	Efficacy	Type II	Type I	
Interim 1	22	0.7921	0.0005	0.0106	0.0005	
Interim 2	60	0.2139	0.0090	0.0548	0.0093	
Final	124	0.0194	0.0194	0.1000	0.0250	

Table 1. Group Sequential Trial Design – Boundary Information

<sup>3 Fleiss JL, B Levin, MC Paik. Statistical Methods for Rates and Proportions, 3rd Ed. John Wiley & Sons, 2003, (Ch. 3, p 61).

ST 800-A

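### The SAS boundary code in SAP 5.4.4 places the second look at 40% information (its comment says 50%) while the plan is 60 of 124 (48.4%), so the code does not return the SAP's boundary table

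*SAP*

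**What the plan says.** SAP 5.4.4 fixes the timing in its text: "Interim analyses will occur when approximately 22 and 60 total subjects have been enrolled with 3-month assessments". Its table, *Group Sequential Trial Design – Boundary Information*, has rows for 22, 60 and 124 evaluable subjects. The look-2 row (n, futility p, efficacy p, cumulative type II, cumulative type I) is "Interim 2 60 0.2139 0.0090 0.0548 0.0093". Protocol Table 3 prints the same figures. On the boundary family, SAP 2.4 says: "A shape parameter of 0.65 will be used, and both boundaries will be non-binding".

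The SAS listing that closes SAP 5.4.4 sets the information levels with "design nstages=3 info=cum(3.6 8 20". Its inline comment gives 3/20, 10/20 and 1.

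For the interim test, SAP 5.4.4 says: "The interim analyses will use an alternative to the critical ratio test given below". The formula that follows is z′, a continuity-corrected difference over an unpooled standard error. The same section says that at 70% v 40% "the chance that the trial will stop for effectiveness at the second interim analysis is about 1 in 3", and that with a Latera rate of 85% "the chance of stopping for effectiveness at the second interim analysis is better than 8 in 10". Protocol 6.8 repeats both chances.

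**The concern.** One section gives three different timings for the second look: 40% in the code, 50% in the comment, and 48.4% in the text and table. The comment also disagrees with the code line it annotates at look 1 (3/20 v 3.6/20).

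The listing stands directly after the table and is headed as boundary code, so it is naturally read as the source of the thresholds. A statistician who runs it to verify them, or adapts it because a look falls at another sample size, would start from a different design. The look-2 efficacy, look-2 futility and final thresholds would all change. For example, a final p-value of 0.020 succeeds under the code's 0.0204 and fails under the table's 0.0194. The SAP does not say which governs.

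The stopping chances are a smaller matter. They describe how the interim plan should behave, so they ought to follow from the test it names.

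**Working it through.** **Inputs.** Triangular boundaries with τ = 0.65, one-sided α = 0.025, β = 0.10 and non-binding futility (SAS listing). Rates 40% v 70% and a maximum of 124 evaluable subjects (SAP 2.4). 1:1 allocation (protocol synopsis). Looks at 22/60/124 (SAP 5.4.4). The calculation was done in Python by recursive numerical integration, not in SAS.

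**Timing on a maximum of 124**

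| Source | Look 1 | Look 2 |
|---|---|---|
| Text and table | 22 (17.7%) | 60 (48.4%) |
| Code 3.6, 8, 20 | 22.3 (18%) | 49.6 (40%) |
| Comment 3/20, 10/20 | 18.6 (15%) | 62 (50%) |

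**Formulas.** At information fraction t, let f(t) = t^(−1/2) + 0.65·t^(1/2).
- Efficacy bound: Z = C·f(t), with C solved for α = 0.025 ignoring futility.
- Futility bound: Z = D·√t − B·f(t), with D and B solved so that the bounds meet at the final look and β = 0.10.
- Total N = 2 × (0.24 + 0.21) × (D/0.30)².

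**Reproducing the table.** With information 3.6, 9.7, 20 (t = 0.18, 0.485, 1), C = 1.2529 and D = 3.5107.
- Look-2 efficacy: f(0.485) = 1.8886, Z = 1.2529 × 1.8886 = 2.366, p = 0.0090.
- Final: Z = 1.2529 × 1.65 = 2.067, p = 0.0194.
- Look-2 futility: B = (3.5107 − 2.0673)/1.65 = 0.8748; Z = 3.5107 × 0.6964 − 0.8748 × 1.8886 = 0.793, p = 0.2139.
- N = 0.9 × (3.5107/0.30)² = 123.25, which rounds up to 124 at 1:1.

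**Comparison**

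| Information | Efficacy p | Futility p | Look-2 cumulative type I / II | N |
|---|---|---|---|---|
| SAP table | 0.0005/0.0090/0.0194 | 0.7921/0.2139/0.0194 | 0.0093 / 0.0548 | 124 |
| 3.6, 9.7, 20 | 0.0005/0.0090/0.0194 | 0.7921/0.2139/0.0194 | 0.0093 / 0.0548 | 123.25 |
| Code: 3.6, 8, 20 | 0.0006/0.0068/0.0204 | 0.7916/0.3195/0.0204 | 0.0071 / 0.0471 | 121.0 |
| Comment: 3, 10, 20 | 0.0002/0.0094/0.0193 | 0.8664/0.1985/0.0193 | 0.0095 / 0.0552 | 122.8 |
| Exactly 22, 60, 124 | 0.0005/0.0090/0.0194 | 0.7987/0.2151/0.0194 | 0.0092 / 0.0546 | 123.2 |

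**A check free of α and of the binding rule.** The ratio of look-2 to final efficacy Z must equal f(t₂)/f(1). The table gives 2.366/2.066 = 1.145. The formula gives 1.207 at t₂ = 0.40, 1.136 at 0.50 and 1.145 at 0.485. No α or binding variant of the printed code can therefore return the table.

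**Effect if the code's thresholds were applied at 22/60/124** (normal model, four-decimal thresholds)

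| | Table | Code |
|---|---|---|
| Type I error (futility ignored) | 0.0251 | 0.0245 |
| Power at 70% v 40% | 0.901 | 0.917 |
| Look-2 futility stop, no difference | 0.58 | 0.48 |
| Look-2 futility stop, 70% v 40% | 0.044 | 0.020 |
| Expected N, no difference | 64.8 | 71.2 |
| Expected N, 70% v 40% | 84.5 | 88.4 |

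**Stopping chances under z′.** Full binomial enumeration with the tabled thresholds. Assumed, because the SAP does not say: 11 and 30 per arm, sign of the difference kept, futility obeyed.

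| Reading | 70% v 40% | 85% v 40% |
|---|---|---|
| Stop at look 2 | 0.39 | 0.67 |
| Stop at look 2, given it is reached | 0.42 | 0.87 |
| Look 2 taken alone | 0.45 | 0.89 |
| Cumulative by look 2 | 0.46 | 0.90 |

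The reading closest to one in three gives 0.67 at 85%, not above 0.8. The readings that exceed 0.8 give 0.42 to 0.46 at 70%. Under Fisher's exact test or a pooled corrected test, stopping at look 2 has probability 0.37 and 0.85, which fits both statements.

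**The case against.** The strongest reply is that nothing depends on the listing. Interim results are compared with boundaries printed as numbers, identically in both documents, and no sentence directs anyone to rerun the code or says that it produced the table. On that view this is a stale listing beside a correct table. Much of this stands: the table is right, the error rates barely move, and calling the code the source of the thresholds is an inference from its heading and position. It does not remove the contradiction. The SAP prints two sets of decision thresholds, one explicitly and one through its code, without ranking them.

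It can also be said that 9.7 is back-fitted, since exactly 22/60/124 gives futility p-values of 0.7987 and 0.2151 rather than 0.7921 and 0.2139. That is fair. The documents do not state 9.7, although 60/124 × 20 = 9.68 makes it the natural rounding. The corrected code therefore has to be run in SAS before it is adopted.

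On the stopping chances, the sentences do not name a test, SAP 2.4 and 5.2 refer only to a one-sided binomial test, and whether 0.42 counts as about one in three is a matter of judgement. The protocol never prints z′, so it does not contradict itself here. What stands is narrower: the figures conflict with the interim test named in SAP 5.4.4, but they are attainable under another test.

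**Conclusion.** The point holds. The code line and its comment are wrong, and the boundary table is right for looks at 22, 60 and 124. Run as printed, the code moves the look-2 efficacy threshold from 0.0090 to 0.0068, the look-2 futility threshold from 0.2139 to 0.3195, and the final threshold from 0.0194 to 0.0204. The practical effect is small, with no inflation of type I error at the planned looks. It should be corrected, but it does not threaten the trial's conclusion.

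This rests on a Python implementation of the triangular boundary rather than PROC SEQDESIGN itself. Its agreement with every boundary and error-spending entry in the table at information 3.6, 9.7 and 20 supports the implementation.

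The secondary point holds in limited form: under z′, and under the stated assumptions on arm sizes, sign and futility, no single reading gives both printed chances.

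**What to change.** In SAP 5.4.4:
1. Change the information levels to `info=cum(3.6 9.7 20)` and the comment to 3.6/20, 9.7/20 and 1.
2. Run the code in SAS and confirm that the output matches the table at four decimals. If it does not, replace the listing with the run that produced the table.
3. State that the boundary table governs.
4. Recompute the two stopping chances under the interim test the SAP names. State the test, and whether each chance is for look 2 alone, conditional on reaching it, or cumulative.

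Protocol 6.8 can take the revised stopping-chance wording at its next amendment.

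The cost is one code line, its comment, one added sentence and the stopping-chance sentences. Thresholds, maximum sample size and enrolment do not change, and no separate protocol amendment or IRB submission is needed.

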#### 5.5 Missing or Incomplete Data

Every effort will be made to minimize the amount of missing data. Recognizing the difficulty of avoiding some missing data, however, data imputation methods with sensitivity imputation analyses will be conducted as secondary analyses for the primary endpoint in the ITT and mITT populations. The robustness of the multiple imputation-based sensitivity analyses for the primary outcome will be tested with a tipping point analysis encompassing all possible imputation outcomes.

As a secondary sensitivity analysis in the ITT and mITT populations, multiple imputation of the primary endpoint will be carried out using the logistic regression approach for a dichotomous outcome with PROC MI in SAS for patients missing data for the 3-month assessment. The following baseline variables will be included in the imputation model as covariates:

- Age
- Gender
- Body Mass Index (BMI)
- Nose Length
- Nose Height
- Nose Width
- Inferior Turbinate Hypertrophy
- Septal Deviation

<sup>4 Yan X, Lee S, Li N. Missing data handling methods in medical device clinical trials. J Biopharm Stat, 19, 1085-98, 2009.

ST 800-A

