This Clinical Investigational Plan (CIP), informed consent forms (ICF), recruitment materials, and all participant materials will be submitted to the Institutional Review Board (IRB) for review and approval. Approval of the CIP and the ICF must be obtained before any subject is enrolled. Any amendment to the CIP will require review and approval by the IRB before the changes are implemented to the study. In addition, all changes to the ICF will be IRB-approved and a determination will be made regarding whether a new consent needs to be obtained from subjects who previously provided consent.

INVESTIGATOR SIGNATURE PAGE

Investigator Name

Title

Site Name

Site Number

Date

I have read the protocol and agree that it contains all necessary details for carrying out this study. I will conduct the study as outlined therein.

I agree to keep records on all subject information (e.g., source documents and informed consent forms), device shipments and return forms, and all other information collected during the study, in accordance with local and national regulations.

Investigator Signature

SYNOPSIS

Study Title	Latera RCT – Latera [®] Absorbable Nasal Implant vs. Sham Control for Lateral Nasal Valve Collapse		
Spirox Protocol Number	CP04		
Investigational Device	Spirox Latera Absorbable Nasal Implant		
ClinicalTrials.gov Identifier	NCT 03400787		
Sponsor	Spirox, Inc. [name]		
Study Purpose	To evaluate the Latera Absorbable Nasal Implant (Latera Implant) Implant versus Sham Control in subjects with nasal valve collapse due to or primarily due to insufficient cartilaginous support of the lateral nasal wall		
Objective	The primary objective of the LATERA RCT is to demonstrate the superiority of the Latera Implant to improve nasal breathing, compared with a Sham Control treatment.		
Phase of Study	Post-market		
Study Design	Randomized (1:1), sham-controlled, single-blind, multicenter pos market trial using an adaptive trial design		
Investigational Sites	Up to 15 investigational sites in the United States, in office-based locations with investigators experienced in standard nasal interventions for airway obstructions and the use of the Latera Implant		
Study Population	The Adaptive Design allows for enrollment of up to 150 subjects with nasal airway obstruction due to or primarily due to nasal valve collapse.		

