3.3. Secondary Endpoints

The following endpoints comprise the secondary endpoints and the time points that each will be assessed:

- Responder Rate at 7 days, 30 days, and 6, 12, 18 and 24 months;
- Frequency of procedure-related adverse events (non-serious and serious), assessed at the index procedure and through the 7-day, 30-day, 3-month, 6-month, 12-month, 18-month, and 24-month follow-up time points;
- Frequency of device-related adverse events (non-serious and serious), assessed at the index procedure and through the 7-day, 30-day, 3-month, 6-month, 12-month, 18-month and 24-month follow-up time points;
- NOSE score, change from baseline, to the 7-day, 30-day, 3-month, 6-month, 12-month, 18-month, and 24-month follow-up time points;
- Visual Analogue Scale (VAS), change from baseline, to the 7-day, 30-day, 3-month, 6-month, 12-month, 18-month, and 24-month follow-up time points;
- Endoscopic lateral wall insufficiency (LWI) score as assessed by independent reviewers, change from baseline to the 3-month and 6-month time points;
- Epworth Sleepiness Scale (ESS) score and Pittsburg Sleepiness Quality Index, change from baseline, to the 7-day, 30-day, 3-month, 6-month, 12-month, 18-month, and 24-month follow-up time points.

All secondary endpoints will be assessed for the Sham Control Arm at two additional visits. The Sham arm will have follow-up visits at 7 days, 30 days, and 3 months after the initial treatment/randomization, and 30 days, 3 months, 6, months, 12 months, 18 months, and 24 months in subjects that cross over.

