5. STUDY PROCEDURES AND FOLLOW-UP EVALUATIONS

5.1. Screening/Baseline Assessment

All patients seeking treatment for nasal obstruction will be screened for eligibility according to the inclusion/exclusion criteria. A member of the site's research team will review the patient's medical history for eligibility and potential inclusion into the study.

The Investigator or their designee will inform the patient about the purpose of the study and will explain the potential benefits and risks of both study arms, the Latera Implant and/or the Sham Control arm. Potential subjects will be counseled as to the nature of their condition. All subjects will have ample time to ask questions.

Patients indicating that they would like to proceed with study participation, and who are willing to comply with the requirements of the study protocol, will be asked to sign an Informed Consent Form (ICF) that has been approved by the governing IRB. Failure to provide written informed consent makes the patient ineligible for the study.

Female patients of childbearing potential will undergo a pregnancy test to verify eligibility. Women of childbearing potential are defined as any female who has experienced menarche and who is NOT permanently sterile or postmenopausal. Postmenopausal is defined as twelve (12) consecutive months with no menses without an alternative medical cause.

Patients will be considered enrolled as study subjects upon signing the ICF and meeting all study eligibility criteria. Once the subject has been enrolled into the study a baseline assessment will be completed.

The following baseline data will be collected at the Screening/Baseline visit prior to the procedure. All data must be recorded in the study specific EDC for Latera RCT within 5 business days.

• Nasal Obstruction Symptom Evaluation (NOSE) scale

- Epworth Sleepiness Scale (ESS)
- Pittsburg Sleep Quality Index (PSQI)
- NAO Breathing Assessment
- Demographic information
- Abbreviated Medical History
- Nasal medical history including risk factors
- Nasal Exam including assessment of the septum and turbinates
- Modified Cottle Maneuver
- Lateral Wall Motion Video
- LateraTM Implants may involve unknown risks to a pregnant woman, an embryo, fetus (unborn baby) or nursing infant. Any female that is pregnant, planning to become pregnant or is breastfeeding a child, cannot participate in this study. All women of childbearing potential will have a pregnancy test done prior to treatment.

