5.3. Follow-Up Assessments

For subjects randomized to the Latera Implant arm, the follow-up evaluations will be at 7 days, 30 days, 3 months, 6 months, 12 months, 18 months, and 24 months post-procedure.

For subjects randomized to the Sham Control arm, the follow-up evaluation will be at 7 days, 30 days, and 3 months. After the 3-month follow-up evaluation, the subject will be eligible to cross over to the Latera Implant arm, if they continue to meet the study inclusion and exclusion criteria. If the subject is eligible to cross over to the Latera Treatment arm, an informed consent addendum will need to be presented to the subject and signed. If the Latera Implants are deployed, the follow-up schedule is restarted and occur at 30 days, 3 months, 6 months, 12 months, 18 months, and 24 months post-Latera Implant procedure. If the study subject does not meet the eligibility criteria or declined to continue participation, the subjects will be exited. See Section 6.2 for analysis implications.

The schedule of study activities (Table 2, page 28, above) specifies the assessments that will be completed at each follow up visit. Below are the descriptions of the PRO assessments and Lateral Wall Motion Video assessment:

Nasal Obstruction Symptom Evaluation (NOSE) scale

The Nasal Obstruction Symptom Evaluation (NOSE) Scale is a Patient-Reported Outcome (PRO) instrument that will be administered to capture subject perception of the degree of nasal airway patency.¹⁷

The NOSE scale is a validated instrument, developed by the American Academy of Otolaryngology— Head and Neck Surgery (AAO-HNS), and has been used in several clinical trials. The scale is brief, easy to complete, and is an important tool for pre- and post-intervention evaluation of symptoms in subjects with nasal obstruction.

Subjects will be asked: "Since your last follow up visit, how much of a problem were the following conditions for you?" Specifically, subjects will be asked to rate their perceptions on the Likert scale with respect to the following characteristics:

- Nasal congestion or stuffiness
- Nasal blockage or obstruction
- Trouble breathing through my nose
- Trouble sleeping
- Unable to get enough air through my nose during exercise or exertion

Subjects will rate their responses using a Likert scale with response options 0, 1, 2, 3 or 4, as follows:

- Not a Problem
- Very Mild Problem
- Moderate problem
- Fairly Bad Problem
- Severe problem

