6.4. Sample Size

The primary analysis will be based on a 1-sided binomial test of proportions. Assuming a Sham Control response rate of 40% and a Latera Treatment response rate of 70% at month 3, a maximum sample size of 124 evaluable subjects is required for 90% power and preserving a 2.5% (one-sided) type I error rate. This study is designed as a group-sequential trial with 2 interim analyses and a final analysis. The stopping boundaries are derived using the Triangular Method [1], which is a special case of Unified Family (Power) boundaries. A shape parameter of 0.65 will be used, and both boundaries will be non-binding.

Interim analyses will occur when approximately 20 and 60 total subjects have been enrolled. The Latera response rate has been observed at approximately 85% in single-arm trials, and is likely to be slightly lower in a single blind setting. Thus, 70% is likely a conservative estimate. The placebo response rate observed in pain trials is approximately 30%, and may be even higher in a procedural setting, so 40% was selected for the control response rate used in the study design calculations.

Assuming up to a 10% drop out rate and a 10% potential retrieval rate, the sample size is adjusted up to 150 subjects will be enrolled to assure adequate sample size with 3 months follow up will be enrolled.

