#### 2.4 Sample Size Considerations

The primary analysis will be based on a 1-sided binomial test of proportions. Assuming a Sham Control response rate of 40% and a Latera Treatment response rate of 70% at month 3, a maximum sample size of 124 evaluable subjects is required for 90% power and preserving a 2.5% (one-sided) type I error rate. This study is designed as a group-sequential trial with 2 interim analyses and a final analysis. The stopping boundaries are derived using the Triangular

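### The imputation model for the 3-month response leaves out the 30-day and 7-day NOSE and VAS scores; adding them is a cheap improvement to a sensitivity analysis

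*SAP*

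**What the plan says.** SAP 5.5 plans multiple imputation of the 3-month response in the ITT and mITT populations, by logistic regression with five imputed data sets, as a secondary sensitivity analysis. "The following baseline variables will be included in the imputation model as covariates": age, gender, BMI, nose length, height and width, turbinate hypertrophy, septal deviation, NOSE, breathing VAS, sleep apnea, nasal surgery and ESS. That makes 13. No post-baseline score is listed, and neither is treatment arm. The same section adds a tipping-point analysis over every possible pattern of the missing outcomes.

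The primary analysis is in the per protocol population, which requires a NOSE score inside the 3-month window, at least for Latera subjects (SAP 4.1.1).

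Early scores exist. Protocol 3.3 lists "NOSE score, change from baseline, to the 7-day, 30-day, 3-month" and later visits, with the same visits for VAS. Protocol 5.3 covers the control arm: "For subjects randomized to the Sham Control arm, the follow-up evaluation will be at 7 days, 30 days, and 3 months". Table 2 of the protocol marks NOSE and VAS at both early visits.

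On baseline anatomy, Protocol 5.1 lists "Nasal Exam including assessment of the septum and turbinates", demographics and an abbreviated medical history. It does not name nose length, height, width or BMI, and Table 2 does not either. The CRFs (Attachment F) appear in the public text only as a heading.

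**The concern.** A subject who reports no benefit at day 30 and then leaves has told the trial something about the likely month-3 outcome, on the instrument that defines the endpoint. The listed model discards it and predicts that subject as if nothing after baseline were known. If leaving depends on early response, the imputed values drift toward the rate seen in those who stayed. The imputation is the plan's only model-based estimate for randomized subjects without a month-3 score. It therefore stays close to the completers' result in the very situation where it should be able to depart from it. Adding treatment arm to the model, which is needed for a separate reason, does not cure this.

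**Working it through.** **The plan's own figures.** The documents give none for the imputation, so the design figure is the anchor: "a maximum sample size of 124 evaluable subjects is required for 90% power and preserving a 2.5% (one-sided) type I error rate", with looks at 22, 60 and 124. A fixed design at 40% v 70% needs [1.96·√(2·0.55·0.45) + 1.2816·√(0.21+0.24)]² / 0.30² = 55.7, so 56 per arm or 112 in all. Simulating the printed boundaries at 62 per arm gives power 0.901 and type I error 0.0251, so 124 reproduces.

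**Inputs from the documents.** "Assuming a Sham Control response rate of 40% and a Latera Treatment response rate of 70% at month 3" (Protocol 6.4); 10% dropout (Protocol 6.4, SAP 2.4); 1:1 allocation (protocol synopsis).

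**Assumptions, not in the documents.** The day-30 response rate equals the month-3 rate p in each arm. The correlation φ between the two responses is 0.4 to 0.8. Dropout depends only on day-30 status. Arm is in the imputation model.

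**Formulas.** P(month-3 response | day-30 responder) = p + φ(1−p). P(month-3 response | day-30 non-responder) = p(1−φ). If a fraction f of a group are day-30 responders, that group's month-3 rate is p + φ(f−p). With arm in the model and baseline covariates uninformative about early response, missing subjects are imputed at the completers' rate.

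**Missing fractions and mix.** The first column gives the dropout among early responders v early non-responders.

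| Arm and dropout | Missing | f, completers | f, missing |
|---|---|---|---|
| Latera 5% v 22% | 0.7·0.05 + 0.3·0.22 = 10.1% | 0.665/0.899 = 0.740 | 0.035/0.101 = 0.347 |
| Latera 2% v 29% | 0.7·0.02 + 0.3·0.29 = 10.1% | 0.686/0.899 = 0.763 | 0.014/0.101 = 0.139 |
| Sham 2% v 15% | 0.4·0.02 + 0.6·0.15 = 9.8% | 0.392/0.902 = 0.435 | 0.008/0.098 = 0.082 |

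**Month-3 response rates, φ = 0.4 to 0.8.**

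| Arm and dropout | Imputed (completers' rate) | True rate of the missing |
|---|---|---|
| Latera 5% v 22% | 71.6-73.2% | 55.9-41.7% |
| Latera 2% v 29% | 72.5-75.0% | 47.5-25.1% |
| Sham 2% v 15% | 41.4-42.8% | 27.3-14.5% |

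Example: Latera 5% v 22% at φ = 0.4 gives 0.70 + 0.4·(0.740−0.70) = 71.6%.

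**Estimated difference (true value 30 points).**

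- Early failures leave both arms: 71.6−41.4 = 30.2 to 73.2−42.8 = 30.4 with the milder Latera pattern; 31.1 to 32.3 with the stronger one.
- Latera only (sham dropout unrelated to response): 71.6−40 = 31.6 up to 75.0−40 = 35.0.
- Sham only: 70−41.4 = 28.6 down to 70−42.8 = 27.2.

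**Simulated imputation.** This used N = 150, five imputations, and 10% dropout per arm, all early non-responders, at φ = 0.3/0.5/0.7.

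| Model | Latera missing imputed at | Difference |
|---|---|---|
| Truth | 0.49/0.35/0.21 | 0.30 |
| As listed (no arm) | about 0.57/0.58/0.59 | 0.275/0.285/0.294 |
| Baseline plus arm | 0.72/0.73/0.75 | 0.306/0.316/0.326 |
| Baseline, arm, 30-day response | 0.49/0.38/0.25 | 0.296/0.302/0.306 |

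With no true effect (40% in both arms, φ = 0.5) and dropout of 15% in Latera and 5% in sham, rejection at one-sided 0.025 is 0.031 as listed, and 0.024 with arm and 30-day response added.

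**The case against.** The strongest reply is that the plan already has a harder test. The tipping-point analysis spans every assignment of the missing outcomes, including all Latera dropouts failing. Suppose 47/67 respond on Latera and 27/68 on sham, with 15 missing of 150. The worst assignment is 47/75 v 34/75 (62.7% v 45.3%). A pooled z-test gives 0.173/0.0814 = 2.13, one-sided p = 0.0166, still inside the final boundary of 0.0194. The continuity-corrected statistic that the SAP prints for the interim analyses gives (0.173−0.0133)/0.0801 = 2.00, p = 0.023, just outside. So any fragility would be visible, and a reader who inferred that the imputation is the plan's only check would be wrong. What remains is narrower: a tipping-point analysis shows where the conclusion turns, but not which missing outcomes are plausible. The day-30 scores bear on that.

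Second, the trial is built to retain subjects to month 3. Protocol 4.4 follows those who withdraw after anesthesia to that visit, subjects stay blinded until then, and sham subjects who remain eligible may cross over afterwards. This gives unhappy subjects a reason to stay and makes strongly one-sided, failure-driven dropout less likely. The point stands, but the plan itself allows for 10% dropout.

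Third, the bias disappears on adding day-30 response partly by construction, because dropout was assumed to depend on that variable alone. True. In practice the addition would reduce the bias without guaranteeing to remove it.

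Fourth, a reader might infer from Protocol 5.1 and Table 2 that the nose dimensions and BMI are not collected, so that the model cannot be fitted. The documents do not support this. The CRFs are not shown, the baseline headings are broad, and Protocol 6.6 says that baseline anatomic characteristics will be presented.

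**Conclusion.** The omission is real and worth repairing, as a cheap improvement. The imputation uses baseline variables only, although an early reading of the endpoint instrument is available in both arms. If early response predicts both dropout and 3-month response, early failures who leave are imputed too favourably. In the ranges above, Latera dropouts are imputed at 72-75% against a true 25-56%.

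The effect on the treatment difference is modest and has no fixed sign: about +0.2 to +2.3 points when early failures leave both arms, +1.6 to +5.0 when they leave Latera only, and −1.4 to −2.8 when they leave sham only. The largest figure needs a correlation of 0.8, a 2% v 29% dropout split, and failure-driven dropout confined to Latera. A reader might infer that the plan favours the device; the documents do not show that. As listed, without arm, the model pulls the difference below 30 points when dropout is equal (0.275-0.294 above).

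All of this rests on an assumed correlation and dropout pattern. The primary per protocol analysis is not altered by it.

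**What to change.** In SAP 5.5:

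1. Add the 30-day NOSE and VAS scores to the imputation model. Impute sequentially, with the early scores before the 3-month responder status.
2. Impute within arm, or add treatment arm as a covariate, since arm is also absent from the list.
3. Add 7-day NOSE once the SAP schedule table is aligned with protocol Table 2. The SAP table, whose row labels are lost in the public text, appears to lack the 7-day NOSE mark that the protocol has. The SAP (12 February 2018) predates the protocol version (23 March 2018), which may explain it.
4. Confirm against the CRF that nose length, height, width and BMI are recorded, and drop any that are not.

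The cost is SAP wording and a few lines of code, with no new data. Subjects missing the 30-day score need one more imputation step, and those who leave before day 30 gain little. The tipping-point analysis stays as planned.
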